key change process is enhancing awareness. Video vignettes that present common behavioral, normative, and control beliefs, constructs from the **Theory of Planned Behavior** (TPB), can address acquisition of a new behavior. For those who are in or move to the *Contemplation* stage, the key necessary change process is to “tip” decisional balance. **Motivational interviewing (MI)** teaches that an efficient and effective strategy for helping to “tip” the decisional balance is to explore and resolve ambivalence, something not typically used in less effective counseling processes, which tend to impose a solution. We will employ elements of motivational interviewing, which we term **MI-informed counseling**, including: collaborating as partners, empathic understanding, autonomy support, and self-efficacy support. Consistent with our conceptual model, a **Risk Reduction** framework for dual protection is incorporated. LARC with condoms is the optimal option, but it is not the only option. Risk reduction frames prevention behaviors along a continuum rather than in binary terms, recognizing opportunities for incremental behavior change, especially when behaviors are suboptimal.⁵⁰ Thus, STI/HIV messages will also center on behaviors including condom use, partner negotiation, limiting the number of sexual partners, STI testing after unprotected sex, avoiding alcohol and drug use, and use of expedited partner therapy. These behaviors reduce risk even among condom users.²⁴ Finally, both women and men will be portrayed in videos to ensure that the educational messages are patient-centered, salient, authentic, and relevant. **Human-Centered Design (HCD)**, a design approach recently applied to health care, ensuring that interventions meet the needs of the community of users, **will be used to create a usable, sustainable intervention.**⁵¹ In HCD, the designer and end-user collaborate to create solutions in an iterative process of rapid prototyping with key stakeholder participation. Resulting interventions are based on available technology, address true barriers, and are matched to a realistic understanding of behaviors, skills, and informational needs. We will use HCD best practices such as iterative low-fidelity prototyping and multiple course corrections before a final solution is achieved.

2. Hypotheses

We hypothesize that post-intervention, patients using *miPlan* will report:

H¹ a significant increase in contraceptive continuation and condom use

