recruitment and minimize clinic interruptions. Training will include how to use the *miPlan* app, identify and address ambivalence, and support strategies for managing anticipated barriers. [name], an experienced MI counselor, will oversee training, providing didactic presentations on core concepts of the TTM, including stages and process of change and decisional balance. [name] will oversee training related to condoms and contraceptive methods.

Aim 2: Conduct a pre/post feasibility, acceptability, and effectiveness assessment of *miPlan* to examine improvement in dual method use, enhancement of contraceptive adherence and continuation, increase of condom use, and decrease of STI/HIV infection.

Recruitment and Enrollment. All research activities will take place at the DCAM at the University of Chicago and select Planned Parenthood-IL clinics(Austin, Englewood, and/or Roseland).. We will pre-test the app and study procedures with 5 participants (compensation=\$50), following the protocol planned for the pilot study. At their clinical visit, participants who meet the inclusion criteria (n=100) will be referred by clinic staff to a trained on-site RA, who will explain the study and complete the informed consent process. Inclusion criteria are: (1) Being AA female and sexually active with a male partner(s) within the past 6 months; (2) Age 15-25 years; (3) Initiating contraception; (4) Not currently pregnant or intending pregnancy within the next 6 months; (5) English speaking; and (6) Not currently using LARC. As Illinois law ensures the rights of minors to receive confidential reproductive health care without parental consent, we will seek a waiver of parental consent for participation of those 15-17 years old.

Pre-Intervention Baseline (T1) Procedures. Participants will complete a 10-15 minute questionnaire on the *miPlan* app (See appendices). The RA will provide a brief orientation to the *miPlan* app. After viewing *miPlan*, participants will be guided through a MI informed conversation using a worksheet to document the discussion on contraceptives knowledge and usage. The completed worksheet will be given to the participant and a copy will be kept for the participant's records. (10 min). The participant will receive educational materials and a strategies worksheet to discuss with their clinician. The participant will also be given an STI test. Participants will be compensated \$30.

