Post-Intervention (T2) Procedures. At 6-weeks post-enrollment, participants will complete a 15-25 minute phone survey to gauge dual method use, contraceptive adherence/uptake, frequency of unprotected penile-vaginal/anal intercourse (PVI/PAI), and risk reduction behaviors. Participants will be compensated \$20.

Follow-Up (T3) Procedures. At 3 months post-enrollment, participants will complete a 15-25 minute in-clinic survey to gauge maintenance of dual protection behaviors, contraceptive adherence/uptake, frequency of penile vaginal intercourse/penile anal intercourse, risk reduction behaviors, decisional balance/self-efficacy, and an STI test. Participants will receive \$40. We will also conduct a 3-month retrospective chart review to capture interceding visits (e.g., initial contraceptive method selection, method switching, etc.) and diagnoses (e.g., pregnancy, STI/HIV). Participants unable to come in to clinic for their followup visit or who do not wish to come to clinic will be offered an at-home STI screening kit, to be mailed to the address they

provide. Participants who wish to be sent a kit will be mailed a endo-cervical screening kit, via USPS priority mail, with pre-paid postage and instructions for using the administering the self swab to themselves and packaging and mailing the completed kit back to Ci3. No identifying information will be included in the mailing, and all costs with mailing and processing will be paid by Ci3. All participants will be offered the at-home screening option upon reaching their three month follow-up event, and can complete the survey over the phone or online.

4. Duration

We are requesting IRB approval for a portion of Aim 1 to develop and pilot test the miPlan app and Aim 2 which cover months 3-21 of the overall study.

5. Location

The study will be conducted at the Duchossois Center for Advanced Medicine (DCAM) at the University of Chicago . The DCAM is home to adult primary and specialty clinics, pediatric specialty clinics, and outpatient diagnostic and treatment facilities of the University of Chicago Medicine. The will also be additional sites at Planned Parenthood-IL clinics, Austin, Englewood, and/or Roseland.

6. Special Precautions

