The primary risks are loss of confidentiality and potential discomfort associated with answering sensitive questions about STIs, HIV, and sexual risk behaviors. All participants will be assigned a unique study identifier. Once all data has been collected, identifying subject information (including name) will be stripped from the database and from transcripts of focus group and in-depth interviews. Informed consents with the subjects' names will be stored at the University of Chicago and only accessible to designated research staff. Consent forms will be stored in a locked filing cabinet in a locked office at the University of Chicago. Reports, manuscripts, and presentations will never include identifying information. With respect to potential discomfort associated with answering sensitive questions, subjects will be informed that they can skip any question they do not want to answer without penalty and that they can opt out of the study at any time without penalty. Participants are informed of these protections in the consent forms and all relevant study documents.

7. Experimental Controls

Not applicable. This is a pre- and post- intervention

8. Type and number of subjects

During Aim 1, we will recruit users in the clinic waiting room (n=7) to use the app prototype in 20 minute sessions, filming their hands as they use it, taking notes as they navigate aloud, and making changes in response to their feedback.

During Aim 2, we will pre-test the app and all study procedures with 5 women. In the pre- and post-intervention, we will recruit 100 young women (ages 15-25) from the waiting room of a gynecology clinic at the University of Chicago and select Planned Parenthood-IL clinics.

9. Statistical Analysis

Feasibility & Acceptability: Descriptive statistics will be used to analyze the proportions and central tendency for satisfaction, helpfulness, appropriateness, and usefulness of *miPlan*.

Effectiveness: Outcome variables will be measured in the following ways: Chi-square or Fisher's Exact Test (categorical variables); *t* test and Mann-Whitney U test (continuous variables); and multinomial logistic and linear regression models. Multinomial logistic regression models will be used based on multiple categories for dual method (e.g., use of oral contraceptive with condoms; implant with condoms; or IUD with condoms). Linear regression and probability models will be used with the categorical dual method collapsed (e.g. any dual method).

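### Section 9 names independent-group tests, and no paired or repeated-measures method, for the effectiveness outcomes of a one-group pre/post study, so real change can be missed

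*Combined protocol and SAP*

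**What the plan says.** **Design.** Section 7 (Experimental Controls) reads "Not applicable. This is a pre- and post- intervention". Aim 2 in section 3 is to "Conduct a pre/post feasibility, acceptability, and effectiveness assessment of" the intervention. Section 8 sets recruitment at 100 women. Section 6 gives each participant a unique study identifier, so her records can be linked across visits.

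**Repeated measurement.**
- T1 has a questionnaire (in an appendix not included in the public document) and an STI test: "The participant will also be given an STI test".
- T2, at 6 weeks, is a "phone survey to gauge dual method use, contraceptive adherence/uptake", among other items.
- T3, at 3 months, is an "in-clinic survey to gauge maintenance of dual protection behaviors, contraceptive adherence/uptake", and also covers "risk reduction behaviors, decisional balance/self-efficacy, and an STI test".

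**Hypotheses.** Section 2 expects, after the intervention, "a significant increase in contraceptive continuation and condom use", and also fewer episodes of unprotected sex.

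**Analysis.** Under Effectiveness, section 9 assigns categorical outcomes to chi-square or Fisher's exact test. For continuous outcomes and models it names a t "test and Mann-Whitney U test (continuous variables); and multinomial logistic and linear regression models". Linear regression and probability models are added for dual method use collapsed to a single category. The rest of section 9 covers covariate screening, complete-case and multiply imputed analyses, outliers, and a comparison of drop-outs with retained women.

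**The concern.** With one group and no control, a pre/post effectiveness contrast compares each woman with herself. Chi-square and Fisher's test for comparing proportions, and Mann-Whitney U, assume two independent groups. The ordinary regressions assume independent rows. The protocol does not mention McNemar's test, the signed-rank test, a paired t test, change scores, GEE, mixed models or clustered standard errors.

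If the named two-sample tests are applied to two visits by the same women, their standard error ignores the covariance between visits. When that covariance is positive, as is usual for repeated reports of behaviour or attitude, the standard error is too large. Confidence intervals are then too wide, p-values too large, and a real change may be reported as no change. With 100 women at most, and attrition expected, the study has little power to spare.

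**Working it through.** The protocol states no power, so there is no figure to reproduce. It also gives no effect size, SD, within-woman correlation, alpha for effectiveness, or retention rate.

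**From the protocol:** 100 women (section 8), one group (section 7), visits T1 to T3 (section 3).

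**Assumed:** two-sided alpha 0.05; equal SD at both visits; change of 0.3 SD; 100 or 80 complete pairs; correlation rho from 0 to 0.7.

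**Continuous outcomes, in SD units**
- True SE of the mean change: sqrt(2(1 − rho)/n)
- SE used by an unpaired test: sqrt(2/n)
- Interval too wide by the factor 1/sqrt(1 − rho)
- True size of the unpaired test: 2[1 − Φ(1.96/sqrt(1 − rho))]
- Paired power: Φ(d/SE_true − 1.96), far tail negligible
- Unpaired power: 1 − Φ((1.96 − d/SE_used)/sqrt(1 − rho)), far tail negligible for rho > 0

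Worked case, n = 100, rho = 0.5, d = 0.3:
- SE_true = sqrt(2 × 0.5/100) = 0.100; SE_used = sqrt(2/100) = 0.141.
- Paired: Φ(3.00 − 1.96) = Φ(1.04) = 85%.
- Unpaired: 1 − Φ((1.96 − 2.12)/0.707) = 59%.
- Size: 2[1 − Φ(2.77)] = 0.56%.
- Change detectable with 80% power: unpaired 1.96 × 0.141 + 0.84 × 0.100 = 0.36 SD; paired 2.80 × 0.100 = 0.28 SD.

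| rho | Interval too wide by | True size, unpaired | Power, 100 pairs: unpaired / paired | Power, 80 pairs: unpaired / paired |
|---|---|---|---|---|
| 0 | 1.00 | 5.0% | 56% / 56% | 47% / 47% |
| 0.3 | 1.20 | 1.9% | 58% / 72% | 47% / 62% |
| 0.5 | 1.41 | 0.56% | 59% / 85% | 47% / 77% |
| 0.7 | 1.83 | 0.035% | 62% / 97% | 46% / 93% |

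These are normal approximations. Simulation with the t tests themselves (20,000 replicates) agrees within about 2 points.

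**Rank tests** (simulation, 4,000 replicates, 100 pairs, 0.3 SD). Mann-Whitney against signed-rank: 54% v 53% at rho 0, 55% v 68% at 0.3, 56% v 83% at 0.5, 57% v 96% at 0.7.

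**Binary outcomes** (simulated pairs, 100 women). The joint probability is p11 = p1·p2 + phi·sqrt(p1(1 − p1)p2(1 − p2)).

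For an assumed rise from 30% to 45% at phi = 0.5:
- p11 = 0.135 + 0.5 × 0.228 = 0.249.
- About 20.1 women in 100 change for the better and 5.1 for the worse.
- McNemar's statistic at the expected counts is 15/sqrt(25.2) = 2.99.
- Chi-square, as a z statistic, is 0.15/sqrt(2 × 0.375 × 0.625/100) = 2.19.

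| Change | phi | Chi-square | McNemar | Exact McNemar |
|---|---|---|---|---|
| 30% to 45% | 0 | 59% | 58% | 54% |
| 30% to 45% | 0.3 | 61% | 75% | 68% |
| 30% to 45% | 0.5 | 63% | 89% | 83% |
| 40% to 55% | 0 | 58% | 56% | 51% |
| 40% to 55% | 0.3 | 60% | 72% | 66% |
| 40% to 55% | 0.5 | 62% | 87% | 81% |

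With no true change (30% at both visits, 100 pairs, phi 0, 0.3 and 0.5), chi-square rejects in 5.2%, 1.8% and 0.6% of runs. Asymptotic McNemar rejects in 5.0% to 5.2%, and exact McNemar in 2.9% to 3.7%.

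**The case against.** **The tests may be meant for between-woman comparisons.** Section 9 never says which visits are compared, and the named tests suit the covariate screening that follows. The multinomial example includes implant and IUD users, who cannot exist at T1 because current LARC users are excluded, so that model probably uses follow-up data with one row per woman. This is a fair reading of the regressions. But the tests are listed under Effectiveness, as the way outcome variables are handled. If only between-woman uses were intended, no test at all is named for the pre/post question.

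**The t test may be paired.** It may, and then the t test figures above do not apply. Its listed non-parametric partner is still Mann-Whitney rather than signed-rank, and categorical outcomes have no paired test. Those losses are of similar size.

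**The documented reach is narrow.** This stands in part. The STI test is the only outcome that the public text confirms at T1 and again later. Its within-woman correlation may be near 0, in which case the loss is near 0. T1 values for condom use, unprotected sex and self-efficacy are inferred from the hypotheses. Contraceptive continuation has no usable T1 value, because the women are initiating contraception. Several behaviours are confirmed at both T2 and T3, but that contrast concerns maintenance.

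**The loss rests on assumptions and can be small.** At rho 0.2 it is 8 points for the t test (57% v 65%, simulated). Exact McNemar is below chi-square at phi 0 (51% v 58% for 40% to 55%) and equal to it at phi 0.2 (60% each). This stands, and the version of McNemar should be named.

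**The error is conservative, this is a pilot, and records can be paired later.** All true, and this limits the harm. It does not make the stated tests right for the stated design.

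**Conclusion.** Section 9 is wrong as written. It assigns effectiveness outcomes in a one-group pre/post study to tests for independent groups and names no method that uses the pairing. The absence of such a method is certain from the text. The size of the loss is not, because it depends on a correlation the protocol does not give. Under the assumptions above, with 100 pairs and a 0.3 SD change, the loss of power in the t test runs from nil at correlation 0, through about 14 points at 0.3 and 26 at 0.5, to about 35 at 0.7. Chi-square and Mann-Whitney lose similar amounts. The direction is towards missed change; it would reverse only if the within-woman correlation were negative. Between-woman uses of the same tests, for covariate screening and for drop-outs against retained women, are sound.

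**What to change.** Revise the Effectiveness paragraph of section 9 to state the visits compared for each outcome and to match the method to them:

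1. **Same woman measured at both visits compared:** McNemar's test for binary outcomes; paired t or Wilcoxon signed-rank for continuous outcomes. State which McNemar version is used. In the simulations the asymptotic version held its nominal 5% and the exact version was conservative.
2. **Any model using more than one visit:** GEE or a mixed model with visit as a predictor and woman as the cluster. For the multinomial dual-method model, use standard errors clustered on woman, or name the single visit analysed.
3. **No usable T1 value** (contraceptive continuation, LARC-based methods): analyse follow-up with one row per woman.
4. **Between-woman comparisons** (covariate screening, drop-outs against retained): keep chi-square or Fisher, unpaired t and Mann-Whitney.

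Pairing corrects the standard error only. With no control group, it does not make a before/after change attributable to the intervention.

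The cost is wording in section 9. No new data, visits or participants are needed, since the study identifier already allows records to be linked.
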